9.1 General Principles

The objective of the data screening is to assess the quantity, quality, and statistical characteristics of the data relative to the requirements of the planned analyses.

9.2 Data Handling and Electronic Transfer of Data

The Amgen Global Study Operations-Data Management (GSO-DM) department will provide all data to be used in the planned analyses. This study will use the RAVE database. The database will be subjected to edit check outlined in the Data

Management Plan (DMP). Central laboratory, PK, antibody, biomarkers, adjudicated events and ECG data is outside of RAVE database. All the datasets to be used for planned analyses will be received from GSO-DM department. Additional details will be provided in the DMP and Data Transfer Plan (DTP).

9.3 Handling of Missing and Incomplete Data

Subjects may miss specific data points for a variety of causes. In general, data could be missing due to a subject's early withdrawal from study, a missed visit, or inability to evaluate an endpoint at a particular point in time. Missing assessment at baseline or on-study will not be imputed.

9.3.1 Missing and Incomplete Dates

Missing and partially missing dates for the following parameters will be queried. In general, the algorithm for imputing missing dates will use the logic below. Unless otherwise specified, Study Day 1 will be the first dose date or randomization date for subjects who never received IP:

- If the year and month are the same as Study Day 1 but the day part is missing, the day will be set to the 1st of the month of Study Day 1.
- If the year is the same as Study Day 1 but the day and month are missing, the day and month will be set to the 1st of January of Study Day 1.
- If the year and day are the same as Study Day 1 but month is missing, the month will be set to January of Study Day 1.
- If the month and day are the same as Study Day 1 but year is missing, the year will be reset to the year of Study Day 1.
- If any of the resulting dates are prior to reference date, the imputed date will be reset to the reference date.
- If day, month and year are all missing, no imputation will be applied.

Partial/missing AE and concomitant medication start dates will be imputed using the algorithm above, with the Study Day 1 being the first dose date. For subjects who are randomized but not dosed, Study Day 1 is defined as the date of randomization. AEs that occurred before first dose as indicated by "Did event start before first dose of investigational product" is marked 'Y', will not be imputed.

9.4 Detection of Bias

This study has been designed to minimize potential bias by allocating treatment groups randomly, assessing endpoints and handling withdrawals without knowledge of the treatment. Other factors that may bias the results of the study include:

- important protocol deviations likely to impact the analysis and interpretation of the efficacy endpoints
- inadvertent breaking of the blind before formal unblinding
- investigational product dosing non-compliance
- the timing of and reasons for early withdrawal from treatment and from study

The incidence of these factors may be assessed. Important protocol deviations will be listed and/or tabulated in the clinical study report (CSR). If necessary, the incidence of other factors will be tabulated.

Any breaking of the blind for individual subjects prior to formal unblinding of the study will be documented in the CSR.

9.5 Outliers

Histograms will be examined to identify outliers in any of the continuous variables used in the analyses. Unexpected and/or unexplained values in categorical data will be identified by utilizing frequency tables.

Extreme data points will be identified during blinded review of the data before final database lock. These data points will be reviewed and queried per the data management or clinical listing review plans. Extreme values will not be excluded from the analyses.

9.6 Distributional Characteristics

Statistical assumptions for the primary and secondary endpoint analyses will be assessed. Continuous endpoints of change from baseline in TET will be analyzed under normality assumption. If the assumptions for the primary analysis are not met, then suitable transformation methods (eg, log transform) will be applied.

9.7 Validation of Statistical Analyses

Programs will be developed and maintained, and output will be verified in accordance with current risk-based quality control procedures.

Tables, figures, and listings will be produced with validated standard macro programs where standard macros can produce the specified outputs.

The production environment for statistical analyses consists of Amgen-supported versions of statistical analysis software; for example, the SAS System version 9.3 or later.

10. Statistical Methods of Analysis

10.1 General Principles

The primary analysis to evaluate the effect of AMG 334 compared to placebo on exercise capacity in subjects with stable angina as measured by TET during an ETT.

The FAS will be used to tabulate demographic data, baseline disease characteristics, and subject disposition. The EAS will include all FAS subjects who received IP and completed the ETT and will be used to analyze the primary and secondary endpoints including the change from baseline in TET, time to onset of ≥ 1 mm ST-segment depression, and time to onset of exercise-induced angina. The Safety Analysis Set will be used to analyze safety endpoints.

Summary statistics by each treatment group will be tabulated at each visit. For continuous endpoints, descriptive statistics will be provided including number of subjects, mean, median, standard deviation, standard error, lower and upper quartiles, minimum, and maximum. For categorical endpoints, frequency, and percentage will be given. Missing data will not be imputed.

Baseline value for exercise duration is the average value of the two qualifying measurements in the screening period.

10.2 Subject Accountability

The number and percent of subjects who were screened, randomized, received IP, received partial or none, completed study, discontinued study and reasons for discontinuing will be summarized by treatment group.

The number and percent of subjects randomized will be tabulated by study site.

Key study dates for the first subject enrolled, last subject enrolled, last subject's end of study, and last subject's ETT will be presented.

Data analysis will occur at the following time points:

The primary analysis will take place after all subjects have completed the on study ETT.

The final analysis will take place after all subjects have completed the study and after the final database lock.

10.3 Important Protocol Deviations

Important Protocol Deviations (IPDs) categories are defined by the study team before the first subject's visit and updated during the IPD reviews throughout the study prior to database lock. These definitions of IPD categories, sub-category codes, and

descriptions will be used during the course of the study. Eligibility deviations are defined in the protocol.

10.4 Demographic and Baseline Characteristics

Demographic (ie, age, age group (based on median cut point), geriatric age group [< 65 , ≥ 65 and ≥ 75], sex, race, ethnicity) and baseline disease characteristics will be summarized by treatment group and overall using descriptive statistics.

If multiple races have been reported for a subject, the subject will be categorized as multiple race.

The following baseline characteristics will also be summarized:

- Weight (kg)
- Height (cm)
- Body Mass Index (BMI, kg/m²)
- Systolic BP (mmHg)
- Diastolic BP (mmHg)
- Heart Rate (beats/min)
- Baseline TET (seconds)
- Concomitant medications of interest (beta blockers, nitrates, calcium channel blockers, ranolazine, ACE inhibitors and angiotensin receptor blockers)

10.5 Efficacy Analyses

Detailed primary, secondary and sensitivity analysis methods are summarized in the table below.

Table 1. Summary of Efficacy Endpoints and Analysis Methods

Endpoint	Primary and Secondary Analysis Methods (EAS)	Sensitivity Analysis Methods
Primary Endpoint		
Change from baseline in TET (seconds)	
 Primary analysis: Two-Way ANOVA model with terms of treatment group and randomization strata (< 7 or ≥ 7 minutes) 	
 Analysis of covariance (ANCOVA) model with terms of treatment group and baseline TET as a continuous measure Repeat primary analysis using the Per Protocol Analysis Set Repeat primary analysis by subgroups, including baseline TET randomization strata, age group and sex (if sample size permits.)
Secondary Endpoints		
Time to onset of exercise-induced angina* (seconds) Time to onset of ≥ 1 mm ST-segment depression (seconds)	
 Primary analysis: K-M log-rank test stratified by Baseline TET strata (< 7 or ≥ 7 minute) Secondary analysis: Cox proportional hazard model including treatment group and baseline TET as a continuous measure	
 Repeat primary and secondary analyses using the Per Protocol Analysis Set Repeat primary and secondary analyses by subgroups including baseline TET randomization strata, age group and sex (if sample size permits)

*includes angina-related symptoms

10.5.1 Analyses of Primary Efficacy Endpoint

The analysis for the primary endpoint, evaluating change from baseline in TET, will be performed using the EAS. The primary hypothesis is that AMG 334 does not substantially decrease exercise capacity, as measured by change from baseline in exercise duration, compared to placebo (ie, the true treatment difference in change from baseline in exercise duration is -90 seconds or more).

In the primary analysis, the primary endpoint will be analyzed using an ANOVA model with terms for treatment group and baseline TET (< 7 or ≥ 7 minutes) randomization strata. Adjusted group means for each treatment group, standard error, 90% CI, difference of group means compared to placebo and associated 90% CIs will be tabulated. If the lower bound of the 90% CI of the difference is more than -90 seconds, then the hypothesis that AMG 334 does not substantially decrease exercise duration will be supported.

Statistical assumptions for the primary endpoint method of analysis will be assessed. If the assumptions for the primary analysis are not met, then nonparametric methods or suitable transformation will be utilized.

Sensitivity analyses described below will be performed for the primary endpoint using the EAS:

- An analysis of covariance (ANCOVA) model including treatment group and baseline TET as a continuous measure
- The primary analysis will be repeated using the PPS

To assess if the treatment effect varies across subgroups of interest, the primary analysis of the primary endpoint will be repeated and will include an interaction term (treatment group* subgroup) in the ANOVA model. If a treatment group*subgroup interaction is observed at a significance level of 0.10, then the primary analysis may be repeated for each level of the subgroup. In addition, reasons for stopping the ETTr will be summarized by treatment group using the EAS.

10.5.2 Analyses of Secondary Efficacy Endpoints

The secondary endpoints are time to onset of exercise-induced angina and time to onset of ≥ 1 mm ST-segment depression.

For time-to-event endpoints, only the first occurrence will be considered. If no event is observed during ETTr, then this subject will be considered as censored at the end of ETTr.

Kaplan-Meier estimates of the event-free time to ST-segment depression and exercise induced angina will be computed and graphically displayed using the EAS. For each endpoint, a stratified (< 7 or ≥ 7 minute randomization strata) log-rank test statistic will be calculated to compare the two treatment groups at a significance level of 0.10.

As a secondary analysis, the hazard ratio and its 90% CI for AMG 334 vs placebo will be estimated using a stratified (< 7 or ≥ 7 minute randomization strata) Cox proportional hazards regression model. The proportional hazards assumption will be assessed by visual inspection for parallel lines over time in the plot of log-negative-log of the survival function vs. log (time) (Hosmer and Lemeshow, 1999). If there is strong evidence of non-proportional hazards for the treatment group, then a piece-wise Cox model (Collett, 2003) or an accelerated failure time (AFT) model will be considered. Regardless of non-proportionality, the main analysis of the primary endpoint will be in terms of the Cox model.

Summary statistics (mean, median, Q1, Q3, and 90% CI) of time to event will be provided by treatment group. The number and percentage of subjects with an observed event will also be provided.

Sensitivity analyses described below will be performed for the secondary endpoints:

- Repeat the secondary analysis (Cox proportional hazards regression) using baseline TET as a continuous measure
- Repeat the primary and secondary analysis using PPS

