### 4.1 Inclusion and Exclusion Criteria

#### 4.1.1 Inclusion Criteria

- 101 Subject has provided informed consent prior to initiation of any study-specific activities/procedures.
- 102 Age  $\geq 18$  to  $\leq 85$  at the time of screening.
- 103 History of chronic stable angina for at least 3 months prior to screening, with at least 1 angina episode/month, on average over that period.
- 104 Ischemic heart disease documented by any one or more of the following:
- a. A history of myocardial infarction (MI) with elevated Creatine kinase - myocardial band (CK-MB), troponin I or T, or the presence of electrocardiogram (ECG) changes consistent with an MI, or
  - b. Coronary angiography demonstrating at least 1 major epicardial coronary artery (eg, left anterior descending, left circumflex, or right coronary artery) with a stenosis of at least 50% diameter or greater but excluding  $> 50\%$  or flow-limiting stenosis of the left main coronary artery unless revascularized by coronary artery bypass grafting, or
  - c. Revascularization procedure (eg, cardiac bypass graft, angioplasty)  $\geq 3$  months prior to screening

Product: Erenumab (AMG 334)  
Protocol Number: 20140254  
Date: 28 October 2016

Page 18 of 63

- 105 Receiving stable doses of cardiac medications (eg, beta blockers, calcium channel blockers, antianginals, etc.) for at least 30 days prior to randomization and that are not expected to change during the study
- 106 Completes 2 qualifying ETTs during screening period (as described for Screening in [Section 7.3.7](#) and [Section 7.3.8](#)). The following ETT qualifications are required:
- a. Limitation of exercise due to symptoms related to myocardial ischemia (such as angina pectoris, chest pain/discomfort, dyspnea, shortness of breath), or  $\geq 3$  mm ST-segment depression
  - b.  $\geq 1.0$  mm ischemic ST-segment depression during exercise performance
  - c. Exercise duration of  $\geq 3$  to  $\leq 12$  minutes, and
  - d.  $\leq 1$  minute difference or within 20% duration (using the longest duration qualifying ETT) in TET between the 2 qualifying ETTs
  - e. ECG tracings from screening ETTs are acceptable to the core ECG laboratory

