### Criteria for Stopping

For each ETT, identify a single primary reason for stopping the test. During the on-study ETT, terminate the ETT as soon as the subject experiences symptom-limited exercise (defined below), or if asymptomatic ST-segment depression  $\geq 3$  mm is observed. The exercise duration is the time required for the subject to reach the exercise-limiting degree of symptoms and no further, thus site staff are not to push, coach or encourage subjects to tolerate symptoms during the ETT which would typically cause them to stop exercise during the course of their usual daily activities.

The following symptoms are reasons for stopping the ETT:

- Unacceptable angina (a condition for which the ETT must be interrupted because of excessive chest pain, rather than because of exercise limitation)
- Shortness of breath or fatigue
- Arrhythmia (eg, sustained ventricular tachycardia, ventricular triplets, high degree of ventricular ectopy, heart block, bradyarrhythmia)
- Excessive elevation of blood pressure (eg, systolic pressure  $> 230$  mmHg or diastolic pressure  $> 115$  mmHg)
- Technical difficulties in monitoring ECG or SBP
- Fall in systolic blood pressure during exercise of  $> 10$  mmHg
- Feeling of dizziness or faintness
- Intolerable musculoskeletal pain or discomfort
- ST-segment elevation  $> 1$  mm in leads without diagnostic Q waves (other than V1 or aVR)
- ST-segment depression  $\geq 3$  mm or marked axis shift

---

Product: Erenumab (AMG 334)  
Protocol Number: 20140254  
Date: 28 October 2016

Page 34 of 63

---

The primary reason for ETT discontinuation should be documented in the CRF.

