6.4 Efficacy Endpoints

Change from baseline in TET

Change from baseline in TET = TET from on-study ETT post-randomization -
baseline TET

Time to Event

Time to event (onset of angina, ≥ 1 mm ST-segment depression) is defined as the time subject received IP to the time of event onset.

Time to event = event onset time – time received investigational product

If no event occurs, then subject will be censored at the ETT stop time.

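### Time to angina is censored at the end of the ETTr even when silent ST depression of 3 mm or more ended the test, and no planned analysis examines this

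*SAP*

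**What the plan says.** SAP 6.4 sets the censoring rule for both time-to-event endpoints: "If no event occurs, then subject will be censored at the ETT stop time". SAP 10.5.2 repeats it: if no event is observed, "then this subject will be considered as censored at the end of" the ETTr. Neither section distinguishes between reasons for stopping. The analyses are Kaplan-Meier curves, a stratified log-rank test at 0.10 and a Cox model.

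Protocol 7.3.9.3 (Criteria for Stopping) tells sites to "terminate the ETT as soon as the subject experiences symptom-limited exercise (defined below), or if asymptomatic ST-segment depression" of 3 mm or more is observed. The list that follows includes shortness of breath or fatigue, arrhythmia and a fall in systolic pressure of more than 10 mmHg. One primary stop reason per test goes on the CRF.

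Inclusion criterion 106a requires "Limitation of exercise due to symptoms related to myocardial ischemia", or ST depression of at least 3 mm. Subjects whose exercise is limited by the ECG and not by symptoms can therefore be enrolled.

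The sensitivity analyses for the secondary endpoints (SAP Table 1 and 10.5.2) are a Cox model with continuous baseline TET, a per-protocol repeat and subgroups. None changes the censoring. SAP 10.5.1 does plan a summary of ETTr stop reasons by arm, and 10.5.2 plans the number and percentage with an event.

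**The concern.** A Kaplan-Meier curve or hazard ratio can be read as describing when angina comes on only if subjects censored at a given time have the same later risk of angina as those still exercising. A subject stopped at 3 mm of silent ST depression was removed by the disease process that produces angina, so equal later risk is doubtful.

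The study asks whether CGRP receptor blockade worsens exercise ischaemia. If AMG 334 made silent ischaemia appear earlier, more treated subjects would leave the angina risk set before they could report angina. The angina result could then err towards reassurance, and nothing planned for that endpoint would test for it.

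**Working it through.** **Figure in the plan.** The documents give no event rate, stop rate or power for the secondary endpoints, so there is no figure for this point to reproduce. The primary sample size does reproduce: with SD 130 s and 27 per arm, SE = 130 × √(2/27) = 35.4 s. A 90% CI (t = 1.675) clears -90 s when the estimate exceeds -90 + 1.675 × 35.4 = -30.7 s. If the true difference is 0, that has probability 0.81, against the stated 80%.

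**Which endpoint the 3 mm stop can censor.** A subject stopped at ≥ 3 mm has already passed 1 mm and is an event on the ST endpoint. The same subject without symptoms is censored on the angina endpoint. The issue therefore concerns time to angina.

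**Check 1: large-sample bias (all times and shifts assumed).** Angina onset has mean 330 s and SD 90 s; the other ischaemic stop has mean 400 s and SD 90 s; both are normal with correlation ρ. The table gives shifts in the median, active minus placebo.

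| Assumed drug shift | ρ | True angina shift | Kaplan-Meier shift | Angina or ischaemic stop |
|---|---|---|---|---|
| angina -30 s, stop -100 s | 0.5 | -30 | about -15 | -55 |
| angina -30 s, stop -100 s | 0.8 | -30 | +1 | -50 |
| angina 0, stop -100 s | 0.5 | 0 | +25 | |
| angina 0, stop -100 s | 0.8 | 0 | +64 | |
| both -60 s | | -60 | -60 | |

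At ρ = 0 there is no bias.

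The unequal shifts imply large changes in how tests end. The share stopped before angina on placebo is Φ(-70 / (90 × √(2(1 - ρ)))): 22% at ρ = 0.5 and 11% at ρ = 0.8. With angina moved by 30 s and stops by 100 s, both means are 300 s and the share becomes 50%.

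**Check 2: trial size.** 27 per arm, log-rank test stratified at 7 minutes, two-sided 0.10 (the SAP does not state sidedness), 2,000 runs per setting. Assumed placebo rates: angina 60–88%, ischaemic stop without angina 5–31%, correlation 0 or 0.7. Time runs from the start of exercise. Ranges cover the four settings.

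| Drug effect | Result | SAP censoring | Ischaemic stop counted as event |
|---|---|---|---|
| none | two-sided error | about 10% | about 10% |
| silent stops 25% earlier, angina unchanged | mean HR | 0.51–0.91 | 1.27–1.79 |
| | harm flagged | 0.1–2.7% | 20–58% |
| | false benefit | 9–43% | |
| both 25% earlier | mean HR | 2.75–3.06 | 2.82–3.25 |
| | harm flagged | 86–91% | 94–98% |

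In the second scenario the ≥ 1 mm ST endpoint had a mean HR of 2.87–3.24 and flagged harm in 93–97% of runs. The 3 mm stop never censored it.

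**What the primary endpoint would show.** In that scenario mean TET fell by 46 to 78 s relative to placebo. The chance of clearing -90 s is 1 - Φ((-30.7 - d)/35.4), with d the true difference: 1 - Φ(0.43) = 33% at d = -46 and 1 - Φ(1.34) = 9% at d = -78.

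**The case against.** **The log-rank and Cox results are not invalid.** With these stops censored they still compare the rate of angina among subjects still exercising, and error stays near 10% when the drug has no effect. This stands. The assumption fails only when the result is read as angina timing, which is how the endpoint is named and likely to be reported.

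**A reader might infer that both secondary endpoints are affected.** The documents do not support that. A 3 mm stop is already an ST event. A stop for another reason before 1 mm could censor the ST endpoint, but criterion 106b required at least 1.0 mm at both qualifying tests and 216d excludes unstable ST depression between screening tests, so such stops should be less common.

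**A reader might infer that every other stop on the list is an ischaemic case wrongly censored.** The SAP Table 1 footnote says the angina endpoint "includes angina-related symptoms", and protocol 9.1.1 names shortness of breath among the symptoms related to angina, so a dyspnoea stop may already be an event. The protocol does not call arrhythmia or the pressure fall ischaemic.

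**A reader might infer that harm would be hidden from the trial.** It would not. The shifts that distort the angina curve also shorten TET, move the ST endpoint, change the stop-reason table and alter the event counts. What remains is narrower: none of these corrects the angina curve, hazard ratio or p-value.

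**The direction is conditional.** The result errs towards reassurance only if silent stops move forward more than angina does.

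**Conclusion.** The point holds for time to onset of exercise-induced angina only. The censoring rule ignores why the test ended, one mandated reason is silent ischaemia, criterion 106a admits subjects limited in that way, and no planned sensitivity analysis addresses it.

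The size cannot be determined from the documents. Under the assumed rates the effect ranges from nothing (equal shifts, or independent times in check 1) to a false favourable result in up to 43% of trials (only silent stops brought forward by 25%, correlation 0.7). The latter needs stops without angina to rise from 20% to 73%, for which the documents offer no support. The primary analysis and the ≥ 1 mm ST endpoint do not depend on the rule for a 3 mm stop. This is a cheap improvement, not a threat to the trial's main conclusion.

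**What to change.** Add one prespecified supportive analysis to SAP 10.5.2: time to the first of angina (including angina-related symptoms) or an ETTr stop with ST depression of 3 mm or more as the recorded primary reason. Any other stop reasons to be counted as ischaemic should be listed in the SAP before unblinding. Use the same stratified log-rank test and stratified Cox model.

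Leave ST depression of ≥ 1 mm out of this composite. It precedes any 3 mm stop and was required at both qualifying tests, so it would dominate and largely repeat the existing ST endpoint.

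Beside the angina result, show the number censored by stop reason and arm.

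The primary stop reason is already on the CRF and already summarised by arm, so no stopping rule or data collection changes. The cost is one extra run and one more supportive result to interpret.

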### 2.2 Study Rationale

During myocardial ischemia, cardiac sensory nerves release neuropeptides, including CGRP, substance P, neurokinin A, and other neurokinins that produce compensatory coronary vasodilation and negative inotropic and chronotropic effects, potentially mitigating the extent and severity of the ischemic response (Burley et al, 2007). The release of CGRP during myocardial ischemia suggests that CGRP blockade may

---

Product: Erenumab (AMG 334)  
Protocol Number: 20140254  
Date: 28 October 2016

Page 14 of 63

interfere with homeostatic cardio protective mechanisms that occur in the setting of acute ischemia.

The hypothesis that blockade of CGRP-receptors does not reduce exercise capacity was tested in an ETT with telcagepant, an orally-administered CGRP receptor antagonist previously under development for the treatment of acute migraine ([Chaitman et al, 2012](#)).

The ETT is an established methodology for detecting the physiologic effect of vasoactive agents such as antianginal drugs and has also been used in safety studies to assess the potential of vasoactive drugs to reduce exercise time. The effects of supra-therapeutic doses of telcagepant on TET were assessed in a double-blind, randomized, placebo-controlled, two-period, crossover study in 60 subjects with stable angina and reproducible exercise-induced angina. No significant between-treatment differences were found in TET, maximum exercise heart rate, or time to > 1-mm ST-segment depression. The results of this study suggest that CGRP blockade does not exacerbate myocardial ischemia.

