#### 2.5 Risk Assessment

There is no direct benefit for individual subjects participating in this study, however there is a potential indirect benefit to participants in this study since they will undergo cardiovascular evaluation and assessments, including ETT, which may provide their treating physician with more detailed information that may improve their care. This study will test the hypothesis that AMG 334 does not significantly decrease exercise capacity in the study population, and, as such, would be supportive of the safe use of AMG 334 as migraine prophylaxis in subjects with, or at risk of, cardiovascular disease.

CONFIDENTIAL

**AMGEN**®

**AMGEN**®

---

Product: Erenumab (AMG 334)  
Protocol Number: 20140254  
Date: 28 October 2016

Page 16 of 63

To date, no evidence of a cardiovascular safety signal has been observed in preclinical, or phase 1, 2, and 3 studies of several investigational products interfering with the CGRP signaling pathway. This body of evidence includes dedicated cardiovascular studies with hemodynamic monitoring.

All subjects participating in the clinical study will be monitored closely for any cardiovascular abnormalities with vital signs assessments, electrocardiograms (ECGs), and physical examinations conducted at screening and before, during, and after the ETT procedures.

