3.1 Study Design

This is a phase 2a, multicenter, randomized, double-blind, placebo-controlled study in subjects with stable angina. At least 54 subjects will be randomized in a 1:1 ratio to receive either a single dose of AMG 334 140 mg or placebo intravenously prior to completing an ETT. Randomization will be stratified by the TET average of the 2 qualifying screening ETTs (< 7 minutes or ≥ 7 minutes). Treatment group will be blinded to the investigator, subjects, and the Amgen study team.

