3.2 Sample Size

The primary endpoint is the change from baseline in TET. Assuming between-subject standard deviation for change from baseline in exercise duration of 130 seconds, with a planned study size of at least 27 subjects in each group and a difference in change from baseline in exercise duration of 0 seconds between AMG 334 group and placebo group, there is an 80% probability (power) that the lower bound of the 90% confidence interval

(CI) will exceed -90 seconds. A margin larger than -60 seconds between groups was required to accommodate the possibility of more than 60 second (up to 20%) difference allowed in qualifying TETs for individual subjects. Because of this within-subject TET variation, a maximum TET difference of 90 seconds between the AMG 334 group and placebo group was considered reasonable in this study. A margin of -90 seconds was selected, which corresponds to the margin used in previous study testing a comparable hypothesis (Patterson, et.al 2005). Twenty-nine subjects are needed in each group if considering 5% dropout.

When approximately 45 subjects have been enrolled, Amgen may conduct a blinded sample size-estimation and may choose to alter the sample size based on the blinded variance in the pooled treatment groups.

4. Study Endpoints and Covariates

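### Both ischaemia onset endpoints rest on a log-rank difference test at 0.10 with no margin or power statement; with at most about 54 events, a non-significant result says little about harm

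*SAP*

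**What the plan says.** SAP 10.5.1 judges the primary endpoint, change from baseline in TET, by whether the lower 90% confidence limit for the treatment difference lies above -90 seconds.

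The two onset endpoints are handled differently. SAP 10.5.2, like protocol 10.5.4, plans Kaplan-Meier curves and, for each endpoint, a stratified "log-rank test statistic will be calculated to compare the two treatment groups at a significance level of 0.10". SAP Table 1 (section 10.5) lists the "K-M log-rank test stratified by Baseline TET strata" as their primary analysis. Whether the test is one- or two-sided is not stated.

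SAP 10.5.2 adds, as a secondary analysis, that "the hazard ratio and its 90% CI for AMG 334 vs placebo will be estimated using a stratified" Cox model, and it makes a Cox model with continuous baseline TET a sensitivity analysis. Table 1 gives the secondary Cox model with continuous baseline TET. Section 10.5.2 also says that the main analysis of the primary endpoint will be in terms of the Cox model, although the primary endpoint is analysed by ANOVA.

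The sample size (SAP 3.2, protocol 10.2) is derived for TET alone: "planned study size of at least 27 subjects in each group", and "Twenty-nine subjects are needed in each group if considering 5% dropout". SAP 6.4 starts the onset clock when investigational product is received.

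**The concern.** Protocol 2.2 gives the scientific worry: CGRP blockade may interfere with protective mechanisms during acute ischaemia. The two onset endpoints address this more directly than TET does. A difference test suits the question poorly, because fewer events or noisier data make a non-significant result more likely, and that result puts no limit on the size of harm.

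The protocol's own background shows how such a result can be read. Of an earlier trial of a CGRP receptor antagonist it reports "No significant between-treatment differences were found in TET, maximum exercise heart rate, or time to > 1-mm ST-segment depression", and then takes the results to suggest that CGRP blockade does not exacerbate ischaemia. If the present trial's log-rank results were read the same way, they could be presented beside a TET result as further reassurance without carrying much information. The hazard ratio interval would carry it, but the plan gives that interval no role in any conclusion and does not define its model in one way.

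**Working it through.** **Inputs from the documents.** 27 per group, so 54 in total (SAP 3.1, 3.2); 1:1 allocation; significance level 0.10 and 90% CI (SAP 10.5.2); for TET only, SD 130 s and margin -90 s (SAP 3.2).

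**Inputs assumed.** The documents give no event rate, no SD for onset times and no sidedness. I take the test as two-sided, to match the 90% CI; event proportions of 100%, 80% and 60% (54, 43 and 32 events); and, where an effect in SD units is needed, a 0.5-SD earlier onset.

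**1. The plan's own figure reproduces.**
- SE = 130 × √(2/27) = 35.4 s.
- Power at a true difference of 0 = Φ(90/35.4 − 1.645) = Φ(0.90) = 0.816, or 0.807 with the noncentral t (stated: 80%).
- 27/0.95 = 28.4, rounded up to 29 per group, as stated.

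No comparable figure exists for the log-rank tests.

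**2. Power of the log-rank test by hazard ratio (HR).** Schoenfeld: power = Φ(½√D × ln HR − 1.645), with D the number of events. For D = 54 and HR 1.5: ½ × 7.348 × 0.405 = 1.490, so Φ(−0.155) = 0.438.

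**3. What an observed HR of 1.0 would leave open.** Upper 90% limit = exp(1.645 × 2/√D). For D = 54: exp(0.448) = 1.56.

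| Events | Power, HR 1.5 | Power, HR 2.0 | Upper 90% limit at observed HR 1.0 |
|---|---|---|---|
| 54 | 44% | 82% | 1.56 |
| 43 | 38% | 74% | 1.65 |
| 32 | 31% | 62% | 1.79 |

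**4. Probability of missing a 0.5-SD earlier onset.** Simulated stratified log-rank test, 27 per arm, two strata, normal onset times, random censoring, 10,000 runs per cell. The lower figure in each cell lets the variable behind the 7-minute split carry half the onset variance; the higher figure lets it carry none.

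| Subjects with events | Missed, two-sided 0.10 | Missed, one-sided 0.10 |
|---|---|---|
| 100% | 37% to 50% | 24% to 35% |
| 80% | 44% to 56% | 31% to 42% |
| 60% | 54% to 64% | 39% to 50% |

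**5. Larger shifts are missed less often.** I also modelled onset as 0.75 × baseline TET plus noise, with baseline TET about normal (mean 420 s, SD 130 s, clipped to 180-720 s), noise SD 80 or 130 s, no censoring and a two-sided 0.10 test. A 60 s earlier onset is missed about 35% (SD 80) to 60% (SD 130) of the time; a 90 s earlier onset about 8% to 32%.

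**6. Clock.** Parts 4 and 5 treat onset as treadmill time. The SAP 6.4 clock also includes the infusion of about 60 minutes and any wait. Variation in that interval would make the same shift in seconds a smaller number of SDs.

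**The case against.** A reader might infer that the plan makes p of 0.10 or more its no-harm result. The documents do not support that. The secondary objective is only to evaluate the effect, SAP section 5 states hypotheses for the primary endpoint alone, and neither 10.5.2 nor protocol 10.5.4 sets a success rule. Nor is non-significance the only outcome compatible with safety: a significantly later onset on AMG 334 would be too.

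Protocol 2.5, which says the study "would be supportive of the safe use of AMG 334 as migraine prophylaxis in subjects with, or at risk of, cardiovascular disease", rests that statement on exercise capacity, so it does not tie safety to the onset endpoints. Protocol 2.2 describes another trial and weighs TET, heart rate and ST depression together; it shows a way of reading, not a rule for this trial.

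It would also be wrong to say that the plan provides no bound. It has no margin, but the 90% CI for the hazard ratio will be reported. The Cox sentence in 10.5.2, apparently a slip in naming the endpoint, even leaves it unclear whether the log-rank test leads.

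The miss rates depend on chosen inputs. At an SD of 130 s, 0.5 SD is 65 s, smaller than the 90 s margin for TET, and part 5 shows better power at 90 s. ST events may be frequent, because inclusion criterion 106b requires ST depression on the qualifying tests.

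All of this stands and lowers the severity. It does not settle which analysis leads, which Cox model is meant or how a non-significant result is to be read. Even with all 54 events, the upper limit at an observed hazard ratio of 1.0 is 1.56.

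**Conclusion.** The point holds as a minor one. The primary analysis of both onset endpoints is a difference test with no margin, power statement or event number, and the more informative hazard ratio interval is secondary, inconsistently described and tied to no conclusion. A non-significant log-rank result would be weak evidence of no harm: power is about 44% at a hazard ratio of 1.5, and an observed ratio of 1.0 leaves a hazard 56% higher (54 events) to 79% higher (32 events) at the upper 90% limit. A 0.5-SD earlier onset is missed roughly 37% to 64% of the time at 27 per arm, or 24% to 50% if the test is one-sided. The event proportions, the effect size and the sidedness are assumptions. The TET conclusion is not affected.

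**What to change.** In SAP 10.5.2 and Table 1:

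- Make the stratified (< 7 / ≥ 7 minutes) Cox hazard ratio with two-sided 90% CI the main analysis of each onset endpoint, and report its upper limit as the bound on harm.
- Use one Cox description in both places, with continuous baseline TET as the sensitivity analysis, and correct the sentence that calls Cox the main analysis of the primary endpoint.
- Keep the log-rank p-value as supportive and state its sidedness.
- State that p of 0.10 or more will not be read as no effect on ischaemia.
- Add the between-group difference in restricted mean onset time with 90% CI, counted from the start of exercise rather than from receipt of product (SAP 6.4), with the truncation time fixed in advance. Present it as an estimate in seconds, not as a test against -90 s: that margin was set for change from baseline in TET, and onset time is not baseline-corrected.

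The cost is SAP wording and one extra output per endpoint, with no new subjects. The downside is that the main secondary result becomes a fairly wide interval.
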